## 1. Background

With changes in dietary habits and lifestyle, colorectal cancer has become the fourth leading cause of cancer-related death worldwide, with a higher incidence in males than females. The disease is increasingly showing trends of higher incidence and younger onset . In China, the incidence of colorectal cancer is growing at an annual rate of approximately 2% , posing a significant burden on the healthcare system and society. Currently, surgical resection remains the primary treatment for colorectal cancer. With the advancement of minimally invasive surgery (MIS), the safety and efficacy of laparoscopic colorectal cancer resection have been widely validated and adopted .

However, the optimal technique for bowel anastomosis remains a subject of debate. Some studies suggest that totally laparoscopic anastomosis better aligns with the principles of MIS and oncological clearance compared to extracorporeal anastomosis . Nevertheless, the complexity, longer operative time, and the requirement for highly experienced surgeons limit its widespread application. Furthermore, there is ongoing debate over side-to-side versus end-to-side anastomosis. Some literature reports suggest that side-to-side anastomosis may be associated with a higher incidence of postoperative bowel obstruction .

On one hand, advances in anatomical understanding—particularly the development of the mesocolic plane theory—and improvements in surgical instruments have significantly extended patient survival and reduced recurrence rates. On the other hand, patients' expectations regarding postoperative quality of life are also increasing. Since the anastomotic technique is closely linked to postoperative bowel function and complications, there is a growing clinical demand to optimize bowel reconstruction in a way that preserves or restores physiological function while ensuring oncologic radicality.

The ileocecal valve (ICV) functions as a sphincteric structure separating the small and large intestines. It regulates the passage of intestinal contents under the influence of hormonal and neural control . Some scholars propose that the concept of the “ileocecal region” better reflects the physiological role of this anatomical structure . For tumors located in the ascending colon or proximal hepatic flexure, resection often includes removal of the ICV and part of the terminal ileum. Current anastomotic techniques rarely address reconstruction of the ICV or its potential impact on postoperative gastrointestinal function.

Existing studies suggest that preserving the ICV during extended right hemicolectomy is both safe and feasible without compromising oncologic outcomes, while also promoting faster bowel function recovery . Although this is a promising direction,

many patients, due to tumor location, still require resection of the ICV, leading to several clinical challenges.

The concept of ICV reconstruction was first proposed by Kellogg in 1918 . Subsequent animal studies demonstrated that ICV reconstruction improved weight gain, prevented reflux, and enhanced nutritional status, indicating potential clinical benefits . Clinically, ICV reconstruction has been applied in pediatric patients with congenital ileocecal valve atresia and in patients undergoing ICV resection for non-malignant reasons, yielding satisfactory results. However, the long-term outcomes remain controversial .

In patients undergoing right hemicolectomy, removal of the ICV compromises the natural bacterial barrier, allowing colonic bacteria to migrate into the terminal ileum and even the proximal small intestine. Under certain conditions, this can lead to small intestinal bacterial overgrowth (SIBO), manifesting as abdominal distension, diarrhea, and severe malabsorption of bile acids, vitamin B12, fatty acids, and other nutrients .

Our research team previously established an animal model using a "Roll-Intussuscepted Sleeve Embedding" (RISE) anastomosis technique, which showed improved outcomes compared to conventional anastomosis. Rats in the RISE group experienced faster weight gain, earlier stool formation, and restoration of gut microbiota closer to preoperative levels.

Based on these findings, reconstructing the function of the ICV during laparoscopic right hemicolectomy may offer a solution to the aforementioned clinical problems. However, to date, no studies have systematically evaluated the clinical efficacy or safety of ICV reconstruction in right hemicolectomy for colon cancer. Therefore, this retrospective cohort study aims to assess the safety, feasibility, and clinical outcomes of an anastomotic technique designed to reconstruct ICV function, with the goal of improving postoperative recovery and quality of life for patients.

## 2. Objectives

This is a retrospective study that systematically collects data from patients who have undergone laparoscopic radical right hemicolectomy for colon cancer in our department. Patients are categorized into two groups based on the type of anastomosis: the conventional anastomosis group and the ileocecal valve function reconstruction group. This study aims to investigate the impact of ileocecal valve (ICV) function reconstruction on postoperative complications and bowel function recovery in patients following right hemicolectomy.

The outcomes of interest include anastomotic leakage, anastomotic bleeding, anastomotic stenosis, wound infection, time to first flatus, time to first defecation, time to stool formation, incidence of postoperative diarrhea, and Bristol Stool Form Scale classification.

## **Primary Objective**

To evaluate the safety and feasibility of an anastomotic technique designed to reconstruct ileocecal valve function during laparoscopic right hemicolectomy.

## **Secondary Objective**

To evaluate the clinical efficacy of ileocecal valve function reconstruction in laparoscopic right hemicolectomy, focusing on postoperative recovery of bowel function and reduction in gastrointestinal complications.

## **3. Study Design**

### **3.1 Overall Study Design**

This study is a retrospective cohort study. Clinical data will be collected and analyzed from patients who underwent laparoscopic radical right hemicolectomy for colon cancer in our department. Patients will be categorized into two groups based on the type of anastomosis: the conventional anastomosis group and the ileocecal valve reconstruction group.

### **3.2 Study Setting and Population**

This is a single-center observational study. All clinical data are derived from patients who have previously undergone laparoscopic radical right hemicolectomy in the Department of General Surgery.

Patients will be grouped according to the type of anastomosis (exposure factor):

#### **Conventional Anastomosis Group:**

[figure not shown]
Conventional anastomosis is defined as follows: After transecting the intestine 10 cm proximal to the ileocecal valve and 10 cm distal to the tumor using a linear stapler, the specimen is removed. The stapled ends are disinfected with alcohol. A side-to-side ileocolic anastomosis is performed using a linear stapler. The common enterotomy is closed with additional reinforcement sutures (3-0 absorbable sutures). Anastomotic integrity, patency, and blood supply are verified to ensure no leakage.

[figure not shown]
#### **Ileocecal Valve Reconstruction Group (RISE Anastomosis):**

This study focuses on a novel anastomotic technique aimed at reconstructing ileocecal valve function, based on literature review and accumulated surgical experience. The method is referred to as Revolute Insert Side-End Ileocecal Valve Reconstruction (RISE-ICVR), or simply the RISE Anastomosis. This technique is designed to recreate the physiological valve structure that separates the bacterial-rich colon from the relatively sterile small intestine, adhering to the principle that "form determines function."

Surgical steps include:

1. After resecting the tumor and relevant bowel segments within oncological safety margins, the terminal ileum is everted at three equidistant points using 3-0 sutures to form an "artificial ileocecal valve."
2. A longitudinal incision of approximately 2 cm is made in the colonic wall, about 2 cm from the stapled colon end, along the taenia coli.
3. After confirming that there is no mesenteric twisting, the ileal stump is inserted into the colonic incision. Three anchoring sutures are placed between the midpoint of each ileal suture and the colonic wall.
4. A barbed suture is then used to continuously suture the ileal stump to the colonic wall, creating a sleeve-like embedded anastomosis while simultaneously closing the mesenteric defect between the bowel segments.

This technique complies with the technical standards outlined in the "Expert Consensus on Digestive Tract Reconstruction After Colorectal Resection." All patients underwent standard laparoscopic radical right hemicolectomy.

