#### **Intraoperative Indicators:**

Total operative time

Anastomosis time

Intraoperative blood loss

Intraoperative blood transfusion volume

Incision length

Proximal and distal resection margins

Total number of lymph nodes harvested

Number of positive lymph nodes

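### RISE versus stapled anastomosis may be confounded with surgeon or period: operator is not listed in Section 3.4 and the surgery window is unclear

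*Protocol*

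**What the plan says.** Only the protocol is at hand. On this point it says the following.

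- **Technique.** Section 3.2 introduces RISE with "This study focuses on a novel anastomotic technique aimed at reconstructing ileocecal valve function, based on literature review and accumulated surgical experience". The join is sewn by hand: after the everting and anchoring stitches, "A barbed suture is then used to continuously suture the ileal stump to the colonic wall". For the comparator, "A side-to-side ileocolic anastomosis is performed using a linear stapler". Section 1 adds that, to date, "no studies have systematically evaluated the clinical efficacy or safety of ICV reconstruction in right hemicolectomy for colon cancer".
- **Groups.** Patients are classified by the anastomosis they received. Section 3.3 gives 30 conventional and 20 RISE patients from one department, found by screening records.
- **Source of cases.** Section 3.2: "All clinical data are derived from patients who have previously undergone laparoscopic radical right hemicolectomy in the Department of General Surgery". The eligibility criteria (3.2.1, 3.2.2) contain no surgery dates, no concurrency rule and no operator requirement.
- **Variables.** Section 3.4 lists total operative time and "Anastomosis time" among the intraoperative indicators. Operator and RISE case order appear nowhere in its lists.
- **Dates.** Section 3.4 ties the collection of data on patients having this operation to the date of ethics approval. Section 4.3 says every included patient had been operated on and sent home before the study started.
- **Analysis.** Section 3.7 gives chi-square and t-tests between the two groups and mentions no adjustment.

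**The concern.** A new hand-sewn join is set against an established stapled one, and nothing in the protocol makes the two groups share surgeons or calendar time. If RISE was done mainly by one surgeon, or mainly after the stapled cases, then a difference in leakage, bleeding, anastomosis time or bowel recovery could belong to the surgeon or the period and not to the technique.

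This is partly a matter of how the comparator is drawn and what is extracted, so it cannot be left wholly to a later analysis plan. That plan cannot use an operator field that was never extracted, and no model separates two factors that coincide completely.

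The primary objective is the safety and feasibility of the technique. For a new technique, feasibility includes whether results change with experience. A single pooled figure for the 20 RISE cases would not show that.

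**Working it through.** **The plan's own figure.** 30 + 20 = 50, as Section 3.3 states. It is a count of eligible records, with no power calculation behind it to reproduce.

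**The surgery window.** The date statement in Section 3.4 can be read in two ways.
- As the start of record extraction, it fits the timeline in Section 7 (records collected June to August 2024). No surgery window is then stated anywhere.
- As the start of the surgery window, it would give both groups a common start. It then conflicts with Section 3.2 (surgery already done) and Section 4.3 (all discharged before the study began), unless all 50 operations fell between approval and study start, which no section says.

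Neither reading gives a usable window.

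**If the two factors overlap only in part.** Assume one two-level factor (surgeon or period), all 20 RISE cases in one level, and *c* of the 30 conventional cases in that same level. In a model with technique and that factor, only those *c* cases inform the technique contrast. The variance relative to the unadjusted 30 v 20 contrast is

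VIF = (1/c + 1/20) / (1/30 + 1/20), and effective N = 50 / VIF.

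| c of 30 | VIF | Effective N |
|---|---|---|
| 0 | not estimable | 0 |
| 5 | 0.2500 / 0.0833 = 3.0 | about 17 |
| 10 | 0.1500 / 0.0833 = 1.8 | about 28 |
| 15 | 0.1167 / 0.0833 = 1.4 | about 36 |
| 20 | 0.1000 / 0.0833 = 1.2 | about 42 |

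At c = 0 the technique and factor columns are identical. The three-column design matrix then has rank 2, and the technique effect cannot be estimated.

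**If the factor is ignored, as in Section 3.7.** Assume no true technique effect, a shift of *d* SD between levels, a share *s* of conventional cases in the other level, and a two-sided test at 0.05 (the protocol does not state sidedness). The bias is s × d, and the noncentrality of the t-test on 48 degrees of freedom is s·d / √(1/30 + 1/20) = s·d / 0.2887.

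| s | Type I error, d = 0.3 | Type I error, d = 0.5 |
|---|---|---|
| 0.50 | 0.08 | 0.14 |
| 0.67 | 0.10 | 0.21 |
| 1.00 | 0.17 | 0.40 |

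These figures apply to a continuous outcome. The shifts and shares are assumptions, since the protocol gives neither.

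**A learning phase.** Assume complication rates of 20% in the first 10 RISE cases and 5% in the last 10. The pooled rate is (10 × 0.20 + 10 × 0.05) / 20 = 12.5%, which describes neither phase. In terms of assumed counts, 2 events in 20 is 10% (exact 95% CI 1.2 to 31.7%) wherever they fall. If both fall in the first half, the halves show 2/10 (2.5 to 55.6%) and 0/10 (0 to 30.8%). Those intervals overlap widely (Fisher's exact two-sided p about 0.47), so 20 cases can show order only descriptively.

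**The case against.** Several stronger readings are tempting, and the protocol does not support them.

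- *Surgery date is not collected.* It is not listed, but it is time zero for the 30-day complications and for the times to flatus, bowel movement and formed stool. It must be available, and RISE case order follows from it.
- *Operator will not be extracted.* The Section 3.4 lists are mostly outcomes. They also omit age, ASA status and tumour site, which eligibility requires. Section 3.5 takes all data from the electronic record, which probably identifies the surgeon. The accurate statement is that operator is not listed.
- *The protocol calls RISE operator-dependent.* The remark in Section 1 that "the complexity, longer operative time, and the requirement for highly experienced surgeons limit its widespread application" is about totally laparoscopic anastomosis in general. Operator dependence of RISE is an inference from its hand-sewn steps.
- *The first RISE cases are among the 20.* No section says so, nor that any surgeon did only one technique.
- *Concurrent controls should be the main comparison.* That is a trade-off. Once both techniques are in use, surgeons may choose by patient, which can add confounding by indication.

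It is also fair to say that case-order displays and restricted comparisons are often left to an analysis plan, and that the effect sizes above are assumed. What remains is that the protocol neither lists operator nor fixes a surgery window, and that it draws the comparator without regard to surgeon or time. Doing all the surgery in one department does not answer this, because a department fixes neither the surgeon nor the period.

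**Conclusion.** The point holds as a cheap improvement. As written, the protocol allows technique to be confounded with surgeon or period, does not list the variable needed to examine this, and leaves the surgery window unclear across Sections 3.2, 3.4 and 4.3. Whether confounding or a learning phase is actually present cannot be told from the document.

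The size depends on the unknown overlap. Under the assumptions above, adjustment costs little if 20 of the 30 conventional cases share the RISE level (VIF 1.2), is expensive if 5 do (VIF 3.0), and is impossible if none do. An unadjusted test of a continuous outcome could have a type I error between about 0.08 and 0.40 across the shifts and shares considered. The conclusion that the study may draw about technique depends on a table of technique by operator and period, which the protocol does not yet make possible to promise.

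**What to change.** 1. Add primary operator to the Section 3.4 list, taken from the existing record, and use the surgery date already needed for the 30-day and time-to-event outcomes.
2. State the surgery window (first and last operation date) for each group, and reconcile Sections 3.2, 3.4 and 4.3.
3. Tabulate technique by operator and by calendar period.
4. Show RISE anastomosis time, operative time and 30-day anastomotic events in case order, labelled as descriptive.
5. Keep the full 30 v 20 comparison. Beside it, as sensitivity analyses, repeat it within operators who did both techniques, and using only conventional cases done on or after the date of the first RISE case.
6. If there is no overlap, state in the report that technique cannot be separated from operator or period.

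**Cost.** One extra field for 50 patients, one table, one case-order display and two restricted comparisons. The restricted comparisons will have wide intervals, and the concurrent one may be more exposed to selection by patient, which is why neither should replace the full comparison.

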### **3.2.1 Inclusion Criteria**

Participants must meet all of the following criteria:

1. Aged between 18 and 80 years;
2. American Society of Anesthesiologists (ASA) physical status score of  $\leq 3$ ;
3. First-time diagnosis of colon cancer located in the appendix, cecum, ascending colon, hepatic flexure, or the right one-third of the transverse colon, including patients requiring additional surgery based on post-endoscopic pathological findings;
4. No history of other gastrointestinal diseases (except for benign conditions such as intestinal polyps or gallstones);
5. Complete and accessible clinical data.

### **3.2.2 Exclusion Criteria**

Participants will be excluded if they meet any of the following conditions:

1. Concurrent diagnosis of other malignant tumors;
2. Presence of infectious diseases or autoimmune diseases (e.g., Crohn's disease);
3. Surgical plan changes resulting in the ileocecal valve not being included in the resection;
4. Incomplete or missing clinical data.

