### **3.3 Sample Size**

This is a retrospective cohort study. Based on screening of the hospital's electronic medical records and application of the predefined inclusion and exclusion criteria, a total of 50 patients were included. Among them, 30 patients underwent conventional anastomosis and 20 patients underwent ileocecal valve reconstruction. All surgeries and follow-up were conducted in the Department of General Surgery, Second Affiliated Hospital of Army Medical University.

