**Follow-up Indicators:**

Anastomotic healing status  
Gastrointestinal contrast imaging (e.g., iodine-based contrast, upper GI barium meal)  
Colonoscopy findings

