### **3.6 Study Endpoints**

**Primary Endpoint:**

Postoperative complications within 30 days, specifically anastomotic leakage, anastomotic bleeding, and anastomotic stenosis.

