## **4.3 Financial Burden to Participants**

All patients included in this study have completed surgery and were discharged prior to study initiation. This study involves retrospective data analysis only and will impose no additional financial burden on participants.

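### Cohort entry depends on undefined completeness of clinical data, judged after outcomes have occurred, so patients can drop out of the 30-day safety endpoint

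*Protocol*

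**What the plan says.** Two eligibility criteria deal with data completeness. Inclusion criterion 5 (Protocol 3.2.1) requires "Complete and accessible clinical data". Exclusion criterion 4 (3.2.2) removes patients with "Incomplete or missing clinical data". Neither names the variables or a time point, and neither is confined to what is needed to establish eligibility or the type of anastomosis.

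The protocol uses the term clinical data broadly. Section 3.4 uses it to introduce the observation indicators, and 3.5 says that it all comes from the hospital's electronic medical record (EMR). The indicators include 30-day complications, readmission, mortality, time to formed stool and stool scores. They also include follow-up items such as colonoscopy and contrast imaging.

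The design is retrospective: "This study is a retrospective cohort study" (3.1). Section 3.3 reports the result of a record screen, with "application of the predefined inclusion and exclusion criteria, a total of 50 patients were included", of whom "30 patients underwent conventional anastomosis and 20 patients underwent ileocecal valve reconstruction". Section 4.3 adds: "All patients included in this study have completed surgery and were discharged prior to study initiation". The primary endpoint (3.6) is "Postoperative complications within 30 days, specifically anastomotic leakage, anastomotic bleeding, and anastomotic stenosis".

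**The concern.** In a retrospective cohort, completeness of the record is a post-operative characteristic, and it can depend on how the patient fared. Someone who died early, was reoperated on or was transferred may have no recorded time to formed stool and no follow-up imaging. On the plain wording, that gap is enough to remove the patient from the whole study, not just from the analysis of the missing item. The patient then also leaves the primary complication count, even if the leak or bleed is fully documented.

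The primary objective is safety, and the endpoint is likely to rest on very few events among 20 RISE patients. If completeness is related to outcome and differs between groups, both the complication rates and their difference are biased. If it is unrelated to outcome, only sample size is lost. The protocol gives no numbers screened or excluded, by group or by reason, so the two cases cannot be told apart.

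**Working it through.** **The plan's own figure.** 30 + 20 = 50, as section 3.3 states. These are counts after exclusions. The protocol gives no event rate, effect size or number excluded, so the size of any bias cannot be computed. What follows shows sensitivity only. The 30 and 20 come from the protocol; all event counts, numbers excluded and retention probabilities are assumptions.

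**1. Adding back excluded patients whose outcome is known.** Difference = RISE risk minus conventional risk. Assume 2/30 conventional and 1/20 RISE patients with an event among those retained.

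| Excluded patients, each with an event | RISE | Conventional | Difference (points) |
|---|---|---|---|
| None | 1/20 = 5.0% | 2/30 = 6.7% | -1.7 |
| One RISE | 2/21 = 9.5% | 2/30 = 6.7% | +2.9 |
| Two RISE | 3/22 = 13.6% | 2/30 = 6.7% | +7.0 |
| One conventional | 1/20 = 5.0% | 3/31 = 9.7% | -4.7 |
| One in each group | 2/21 = 9.5% | 3/31 = 9.7% | -0.2 |

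The sign depends on the group in which the exclusions fell.

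**2. Excluded patients whose outcome is unknown (best and worst case for RISE).**
- One per group: from 1/21 - 3/31 = -4.9 to 2/21 - 2/31 = +3.1 points.
- Two per group: from 1/22 - 4/32 = -8.0 to 3/22 - 2/32 = +7.4 points.

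**3. RISE group alone.** Exact (Clopper-Pearson) two-sided 95% upper limits: 0/20 gives 16.8%. If one excluded patient had an event, 1/21 gives 23.8%; if two did, 2/22 gives 29.2%. The point estimate moves from 0% to 4.8% and 9.1%.

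**4. Expected bias within one group.** Let p be the true risk, and r1 and r0 the probabilities of a complete record with and without an event. The risk among retained patients is p·r1 / (p·r1 + (1 - p)·r0). With p = 0.10:
- r1 = 0.70, r0 = 0.95: 0.070 / (0.070 + 0.855) = 7.6%.
- r1 = 0.50, r0 = 0.95: 0.050 / (0.050 + 0.855) = 5.5%.
- r1 = 0.95, r0 = 0.70: 0.095 / (0.095 + 0.630) = 13.1%.

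The first two cases understate the risk and the third overstates it. The third could arise if patients with complications are followed more closely and so have fuller records.

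**The case against.** - **The protocol lists mortality, reoperation and readmission as indicators.** Dropping patients because they died or were reoperated on would defeat those indicators, so completeness may mean only that the chart is usable and the 30-day outcome retrievable. This is a reasonable reading of the intent. But the protocol nowhere says that such patients are kept when other items are missing, and the criteria as worded do not keep them.
- **No exclusion for incomplete data is shown to have occurred.** Surgery and follow-up took place in one department, which limits loss through transfer. This stands as a limit on plausibility. It describes the patients who were included and says nothing about those who were not.
- **The timing is not fully pinned down.** Discharge before study start does not prove that 30 days had passed for everyone, and section 3.4 speaks of collection from ethics approval onward. That sentence conflicts with 3.1, 3.3 and 4.3 and should be reconciled, but it does not narrow the criteria. Section 3.3 already puts both the operations and the follow-up in the past.
- **The illustrated shifts are small beside sampling error.** For 2/30 against 1/20 the Newcombe 95% interval is about -17 to +18 points, wider than every shift shown. That is correct, and no conclusion is shown to reverse. Sampling error is visible in the interval, however, whereas selection at entry is not.
- **Exclusion counts belong in the report, and missing-data analyses in an SAP.** This is fair for those two items. It does not reach the eligibility rule itself, because an SAP handles missing values in patients who are in the cohort and cannot restore those removed at entry.

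**Conclusion.** The concern holds. The two criteria are current text, are unrestricted, and were applied to the records of patients already operated on and discharged. Followed as written, they allow patients to leave the 30-day safety endpoint on the strength of post-operative information.

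The direction and size of the effect are unknown, and whether it acted at all cannot be judged from the protocol. Under the assumed counts, a single excluded patient with an event moves the difference by 3.0 points (-1.7 to -4.7) if conventional, or by about 4.5 points (1/20 to 2/21) if RISE, enough to change its sign. This is a defect worth correcting before the results are relied on. Confidence is medium, because it rests on reading the criteria literally and on there being excluded patients at all.

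**What to change.** 1. Reword inclusion 5 and exclusion 4 so that only missing eligibility or anastomosis-type data prevent entry.
2. Repeat the EMR screen under that wording and keep all other consecutive eligible operated patients, including any in-hospital deaths.
3. Count the 30-day primary endpoint in all of them. Treat an unrecorded recovery time or follow-up item as missing for that endpoint only.
4. In the report or SAP, give exclusions per group with reasons and known primary outcomes, and add a best/worst-case analysis for unknown primary outcomes.

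Steps 1 to 3 are the core; step 4 lets a reader judge what remains. The cost is two reworded criteria, one repeated record screen and one sensitivity analysis, with no new procedures. The downside is that the 30 and 20 may change and some secondary endpoints will have missing values to report.
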